2. REPORTING OF ADVERSE EVENTS

Safety: Patients will be monitored for adverse events on a daily basis. Adverse events will be reported to the Institutional Review Board (IRB), data safety officer and contact MPI [name] immediately. In our prior work, we have not experienced any adverse events related to the study protocols. All infection control guidelines will be followed based on each hospital's policy. Patient risks will be minimized through use of quality electronic devices, regular cleaning and maintenance. Lastly, given the high-intensity nature of the ICU, all patients will receive benefit from frequent monitoring in the ICU as part of routine care.

Study Withdrawal/Discontinuation: Participants who wish to withdraw from the study will notify the study team verbally during study interactions or via letter as outlined in the HIPAA authorization document.

3. STATISTICAL CONSIDERATIONS

Statistical Analyses: We will compare baseline patients' demographic characteristics (age, gender, race and levels of education) between the intervention and control group using two sample t-tests for continuous variables and Chi-square tests for categorical variables to determine whether the two groups are balanced in these variables. Variables that are found to be unbalanced will be included as covariates in all models comparing outcomes between the two groups. Intention to treat approach will be used in all analyses.

a. Primary Specific Aim: Delirium/coma free days by day 7 will be compared using analysis of covariance (ANCOVA) model with group (intervention versus control) as the independent variable while adjusting for the baseline patients' demographic variables not balanced between the two groups. For patients discharged before day 7, the days from discharge to day 7 will be counted as delirium/coma free. For patients who died before day 7, 0 delirium/coma free days will be counted from date of death to day 7. We have used the same approach in our previous trials and this approach is able to appropriately handle potential missing data due to discharge or death of patients before day 7.¹⁷

Secondary Specific Aim 1: Mixed effects models will be used to compare delirium severity (CAM-ICU-7), pain (CPOT) and anxiety scores (VAS-A) measured twice daily from randomization to day 7, time of death or discharge. In each of the models, repeated CAM-ICU-7, CPOT or VAS-A scores will be the outcome variable respectively. Group, time, group and time interactions will be included as independent variables while adjusting for potential baseline covariates. Significant group and time interactions will indicate differences in changes of these outcomes between the two groups. Post-hoc analyses will be conducted to determine the earliest times when significant differences between these outcomes can be detected. We will compare various variance covariance structures including autoregressive (AR) and variance components blocked by time of the day (am versus pm) using the likelihood ratio tests to determine the most appropriate covariance structure. We will also examine potential non-linear trajectories of change in these outcomes by including quadratic time in the models and by fitting spline models.

- **b. Secondary Specific Aim 2:** ANCOVA models will be used to compare IU-TBANS, PHQ-9, and GAD-7 collected at three months post hospital discharge with group as the independent variable while adjusting for potential baseline covariates.
- **c. Missing Data:** We expect up to 20% of patients who may not complete the primary outcome at day 7 due to death in the ICU or discharge before day 7. We will conduct sensitivity analyses with varying assumptions for the patients with missing outcomes to determine the robustness of our findings. The mixed effects model we propose for Secondary Aim 1 is robust to the missing at random assumption and is unbiased if we include all relevant covariates in the model. We will also compare baseline characteristics of patients with 3-month

assessment and those who are lost to follow-up and adjust for the variables associated with missing data to ensure unbiased estimation and inference.

d. Sex as a Biological Variable: Both male and female patients will be included in the trial. We do not anticipate treatment efficacy will differ by sex. We will include sex as a covariate in each analysis to

determine whether estimated treatment effects differ by sex.

e.Sample Size and Power: Sample size estimation is based on the observed effect size from our pilot data where the intervention group had higher delirium/coma free days from the control group with estimated effect size of 0.52. Using two sample t-test, we estimate that we will need 128 total patients with complete data to detect an effect size of 0.5SD or higher at α =0.05. For robustness of results, we also estimated power if we assume Poisson distribution for mean delirium/coma free days with a total 128 patients observed at day 7, we will have 98.7% power to detect group difference at α =0.05 using the nonparametric Wilcoxon test. Allowing up to 20% attrition rate for patients dropping out before day 7, we will enroll 160 total patients for this trial (80 per group).

For Aim 2, for anxiety measured by VAS-A, we estimated power using results published by Chlan et al³¹ where the author reported (1) changes in VAS-A in both the music and control groups appear linear; and (2) the music group showed an average difference of 11 points (SD=6.48) in VAS-A scores between the two groups and the noise canceling headphones group had no-significant change over time. Assuming 128 total patients complete anxiety evaluation by day 7, a daily decrease of 0.03SD on VAS-A in the music group and no decrease in the control group, we will have 83.5% power in detecting a group and time interaction in the repeated measure model at α =0.05 assuming a first order autoregressive correlation structure with 0.4 for measurements one day apart. For pain, assuming a baseline mean of 0.54 for both groups (SD=0.63), a daily decrease of 0.2SD on CPOT in the music group and no decrease in the attention control group, we will have 80.6% power to detect a group and time interaction in a mixed effect model. We will also have 80.6% power to detect a significant interaction assuming similar trajectories for CAM-ICU-7 in the two groups. For Aim 3, we will have 80% power to detect an effect size of 0.5SD between the two groups using two sample *t*-test at α =0.05. The power estimates were conducted using the Power and GLMPower procedures in SAS 9.4.

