4. INCLUSION/EXCLUSION CRITERIA

DDM Inclusion and Exclusion Criteria					
Inclusion Criteria	Exclusion Criteria				
-Age 50 years or older -English speaking -Admitted to the intensive care unit (medical or surgical) -Expected mechanical ventilator support for ≥48 hours -Consentable through a legally authorized representative -Have access to a telephone	-History of dementing illnesses and other neurodegenerative diseases such as Alzheimer's disease or vascular dementia -Psychiatric illness which is not well controlled -Alcohol withdrawal symptoms/concern for withdrawal -Suspected or confirmed drug intoxication/overdose -Traumatic brain injury, ischemic or hemorrhagic cerebrovascular accident, or undergoing neurosurgery -Uncorrected hearing or vision impairment including legal blindness -Incarcerated at the time of study enrollment -Enrolled in another clinical trial which does not permit co-enrollment				
	-Any medical condition precluding safe use of headphones such as: skin breakdown, burns, facial or skull fractures				

5. ENROLLMENT and RANDOMIZATION

Clinical Settings and Study Population: Patients will be recruited from two Indianapolis Hospital systems: Eskenazi Health and Indiana University Health. Patients will also be recruited from Mayo Clinic Rochester.

Recruitment Targets: Final study sample will comprise 160 mechanically ventilated older adults ≥50 years of age.

Screening and Enrollment: Research staff will review the electronic medical records of ICU patients daily for eligibility. Eligible patients' clinical teams will be approached if necessary to confirm eligibility. Eligible individuals (those who meet inclusion criteria and do not meet any exclusion criteria) will be screened up to twice per day for delirium until approached for the study using the CAM-ICU-7. Once eligibility is confirmed, the research team will approach patients or their legally authorized representatives for consent depending on patients' clinical status. Patients consented through their legally authorized representative will be reconsented once clinically able.

Randomization: Using a computer-generated list of random numbers created by study statistician, participants will be randomized by permuted block with varying block sizes. Randomization will occur after consent in a 1:1 manner and will be stratified based on hospital location.

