3. PROTECTION OF HUMAN SUBJECTS

1. Risks to Human Subjects:

1.a. Human Subjects Involvement, Characteristics, and Design: 80% of older adults develop delirium during their ICU stay. Presence of delirium predisposes older adults to immediate in-hospital complications including a longer length of ICU and hospital stay, increased risk of in-patient mortality and elevated costs of care. In addition, ICU delirium is associated with long-term post-discharge complications such as development of cognitive impairment and dementia. Our team is proposing to conduct a randomized clinical trial called "Decreasing Delirium through Music (DDM) in Critically III Older Adults" to evaluate the efficacy of a sevenday slow-tempo music intervention on the primary outcome of delirium/coma free days among mechanically-ventilated older adults admitted to the ICU.

The target population will be English-speaking; mechanically ventilated adults aged 50 and older who have been admitted to the intensive care unit in either Eskenazi Health or Methodist Hospital in Indianapolis or the Mayo Clinic in Rochester. The intervention comprises slow-tempo relaxing music versus a silence track attention control delivered twice daily for seven days. The primary outcomes will be delirium/coma free days. The enrolled population will also include women and minorities who meet the inclusion criteria. Subjects will be excluded as follows: [1] History of dementing illnesses and other neurodegenerative diseases such as Alzheimer's disease or vascular dementia; [2] Psychiatric illness which is not well controlled [3] Alcohol withdrawal symptoms/concern for withdrawal; [4] Suspected or confirmed drug intoxication/overdose, [5] Traumatic brain injury, ischemic or hemorrhagic cerebrovascular accident, or undergoing neurosurgery; [6] Uncorrected hearing or vision impairment including legal blindness; [7] Incarcerated at the time of study enrollment, [8] Enrolled in another clinical trial which does not permit co-enrollment

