Exploratory Aim 2: Determine whether the DDM treatment is associated with slower progression of ADRD pathology in older adult ICU survivors as compared to attention control. Hypothesis 2a: Patients in the DDM treatment group will have slower progression in measures of neurodegeneration (lower level of neurofilament light (NfL), phosphorylated tau-181 (p-tau 181), glial fibrillary acidic protein (GFAP), and S100B), AD pathology (higher levels of Aβ42/Aβ40), vascular pathology (lower levels of C-reactive protein (CRP))⁸ and inflammation (lower levels of interleukins (IL)-1, 6, and 8) as measured by blood-based biomarkers collected in the ICU and 3, 6 and 12 months after hospital discharge, compared to those in the attention control group. Hypothesis 2b: These differences in progression of ADRD pathology between the DDM treatment versus control group will be due, in part, to the DDM treatment decreasing the duration and severity of ICU delirium during the index ICU stay.

4. Exploratory Aims Statistical Considerations added (1,2)

Exploratory Aim 1: Mixed effects models will be used with repeated IUTBANS scores (collected at baseline, 6 months and 12 months as the outcome measures), group, time, and a group and time interaction as independent variables while adjusting for stratification variables and other potential baseline covariates found to be significantly different in univariate comparisons. A significant interaction between group and time would indicate differences in changes of cognitive functions over time between the two groups.

Exploratory Aim 2: Changes in the biomarkers will be calculated and used as the dependent variables in ANCOVA models with group as the independent variable and adjusting for stratification variables and baseline covariates that are found to be different among the groups in univariate comparisons. Mixed effects models will be used to explore the association between oxidative stress biomarkers at ICU admission and those collected at 3, 6-, and 12- months post discharge.

5. Revised Figure 3: DDM Trial Flow Chart

6. Revised Table Time-line of Data Collection and Outcomes Assessments

			ata Collection a					
Co	Method of Collection	ne-line of Data Collection and Outcome ICU Phase			Hospital Discharge	Post Hospital Discharge		
		Enrollment	Intervention Phase	Post- intervention phase		3 months	6 months	12 months
Demographics (Age, race, gender, education, Insurance)	EMR	Х						
Clinical Data (lab	EMR	Х						

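### The primary ANCOVA omits the hospital stratum and enrolment APACHE II and picks its demographic covariates by baseline tests; a fixed covariate set would gain precision at no cost

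*Combined protocol and SAP*

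**What the plan says.** Section 5 (Enrollment and Randomization) sets the allocation: "Randomization will occur after consent in a 1:1 manner and will be stratified based on hospital location". The human subjects section names three locations: "Eskenazi Health or Methodist Hospital in Indianapolis or the Mayo Clinic in Rochester".

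Section 3 (Statistical Considerations) compares age, gender, race and education between arms by t-tests and chi-square tests, and then: "Variables that are found to be unbalanced will be included as covariates in all models comparing outcomes between the two groups". The primary model is an ANCOVA on group, adjusted for the "demographic variables not balanced between the two groups". No p-value or standardised difference defines imbalance.

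Paragraph d of the same section fixes one covariate: "We will include sex as a covariate in each analysis". Its stated purpose is to learn whether the treatment effect varies with sex. Gender is nevertheless also on the list to be screened.

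The secondary aims adjust for baseline covariates that are not named. The 5/22/2023 amendment does use the stratum in its exploratory models: Exploratory Aim 1 by "adjusting for stratification variables and other potential baseline covariates found to be significantly different in univariate comparisons" and Exploratory Aim 2 by "adjusting for stratification variables and baseline covariates that are found to be different among the groups in univariate comparisons".

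Both data-collection tables list APACHE II at enrolment. Section 6 (Study Procedures, a) says that variation in self-directed listening will serve as a covariate in later analyses, without saying which.

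**The concern.** Four features of the primary model looked weak.

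- **Stratum omitted.** Stratified blocks balance the arms within hospital, so differences between hospitals drop out of the true variance of the treatment contrast. A model without hospital still counts them as residual noise. Its standard error is then too large and its test conservative.
- **Severity omitted.** Only demographics are screened, so a severity score already collected at enrolment has no route into the model.
- **Selection by baseline test.** In a randomised trial these tests can flag only chance differences and say nothing about whether a variable predicts outcome. The final model stays unknown until baseline data are compared by arm against an unstated cut-off.
- **Set not explicitly closed.** Self-directed listening is measured after randomisation, and the analyses in which it will be a covariate are not identified.

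A related mismatch is that a main effect of sex shifts the outcome level for men and women. It cannot show whether the treatment effect differs between them.

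At stake are some power already paid for, a primary analysis fixed in advance, and an answer to the sex question.

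**Working it through.** **1. The plan's own figure.** Inputs from Section 3, paragraph e: effect 0.5 SD, α=0.05 (two-sided assumed), two-sample t-test, 128 complete, 20% attrition. The noncentral t at 80% power gives 63.8, so 64 per arm, or 128 in total, with power 80.1%. Then 128/(1−0.20)=160. Both stated figures reproduce. With 80 per arm analysed, power is 88.2%.

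N=160 is the nearer figure for the primary outcome, because days after early discharge or death are assigned rather than missing: "For patients discharged before day 7, the days from discharge to day 7 will be counted as delirium/coma free", and days after death score zero.

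**2. Omitting hospital.** The share of outcome variance due to hospital is not in the documents; 5, 10 and 20% are assumed. The model's standard error exceeds the true one by a factor 1/√(1−share), so the true type I error is 2×[1−Φ(1.96/√(1−share))]:

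- 5%: 1.96/√0.95=2.011, giving 4.43%
- 10%: 1.96/√0.90=2.066, giving 3.88%
- 20%: 1.96/√0.80=2.191, giving 2.84%

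A simulation of 20,000 trials per setting (three equal hospitals, permuted blocks of 2, 4 and 6 within hospital) gave 4.3/3.8/3.0% at N=128 and 4.8/3.9/2.8% at N=160. Simulated power at 0.5 SD:

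| Hospital share | N=128 without / with hospital | N=160 without / with hospital |
|---|---|---|
| 5% | 80.7 / 82.1% | 88.8 / 89.7% |
| 10% | 81.4 / 84.2% | 89.5 / 91.3% |
| 20% | 82.6 / 88.1% | 90.2 / 93.8% |

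**3. Adding prognostic baseline covariates.** R² is not in the documents; 0.10, 0.20 and 0.30 are assumed. The effective size becomes d=0.5/√(1−R²), that is 0.527, 0.559 and 0.598:

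| R² | Power, 64 per arm | Power, 80 per arm |
|---|---|---|
| 0 | 80.1% | 88.2% |
| 0.10 | 84.1% | 91.2% |
| 0.20 | 88.1% | 94.0% |
| 0.30 | 91.8% | 96.4% |

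The tables in steps 2 and 3 are separate illustrations and must not be added. A joint simulation at N=128 (2,000 trials per setting, screening at p<0.05, uninformative demographics) compared the planned rule with a model holding both hospital and APACHE II. Power was 82% against 89% when hospital explained 5% and APACHE II 15% of the variance, and 81% against 92% at 10% and 20%. When each explained 5%, it was 80% against 83%.

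**4. Chance selection.** With sex fixed, three variables remain to be screened (age, race, education). Treating the tests as independent, the chance that at least one enters by chance alone is 1−(1−a)³:

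- a=0.01: 3.0%
- a=0.05: 14.3%
- a=0.10: 27.1%
- a=0.20: 48.8%

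**5. Sex interaction.** With an assumed equal sex split there are four cells of N/4, so the standard error of the difference in effects is √(4/(N/4)) SD: 0.354 at N=128 and 0.316 at N=160. For a difference of 0.5 SD between the sexes, on N−4 degrees of freedom, power is 29% and 35%.

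**The case against.** The plan is valid as written, and every gain rests on quantities the documents do not give. At N=160 the hospital gain is 0.9, 1.8 and 3.6 points, and the largest needs a 20% hospital share. Nothing in the documents shows that APACHE II predicts delirium/coma free days. The R² that matters is the increment over a model that already holds sex. The calculations also assume normal errors for a bounded count of 0 to 7 days. All of this stands, which is why the figures are illustrative ranges.

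A 5% cut-off is the natural reading: 0.05 is the only α in the documents, and the text for Exploratory Aim 1 refers to significant differences. On that reading only the 14.3% figure applies. Still, the primary section does not state a cut-off, and any cut-off would select on chance imbalance rather than prognosis.

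Section 6 does not name the primary analysis when it mentions listening time, and the primary model is defined without it. That is right, so this part calls for one clarifying sentence and no more.

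The tables give neither a scoring window nor completeness for APACHE II, and the intervention starts straight after enrolment. That is a fair condition on using it, and it is carried into the fix.

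None of these points supplies a reason to leave the stratum out of the primary model while adjusting for it in the exploratory ones.

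**Conclusion.** The concern holds as an improvement in efficiency and pre-specification that should be made. It does not show bias, type I inflation or a wrong sample size.

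The textual findings need no assumption: hospital and APACHE II cannot enter the primary model, the rule for other covariates depends on baseline comparisons with no stated cut-off, gender is both screened and fixed, and the stated sex model cannot answer the stated sex question.

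The size does rest on assumptions. For hospital alone, power forgone is about 1 to 4 points at N=160 and 1 to 6 at N=128, over variance shares of 5 to 20% and three equal strata. For covariates with R² of 0.10 to 0.30, it is about 3 to 8 points at N=160 and 4 to 12 at N=128. At the low end the gain is small.

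**What to change.** Before unblinding, amend the SAP as follows.

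- Name one covariate set for the primary ANCOVA and carry it to the secondary models: hospital (as randomised), age, sex and APACHE II. Confirm that APACHE II is complete and scored from data before randomisation.
- State that listening time after randomisation is not in the primary model.
- Drop the baseline significance tests as a selection rule, keep the baseline table descriptive, and remove the conflict between screening gender and fixing sex.
- Add delirium/coma status before randomisation only if the screening CAM-ICU-7 and RASS prove to be recorded and usable for all randomised patients. The schedules show no enrolment entry for them.
- Address the sex question with a group-by-sex term in a supportive model, reported as an estimate with its interval, since power for it is low.

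The cost is SAP wording and a few degrees of freedom among 160 patients. Hospital, age, sex and APACHE II are already scheduled for collection, so no patients or visits are added.

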Primary Specific Aim: Test the efficacy of music intervention in *improving delirium/coma free days* among mechanically ventilated patients as compared to attention control. Hypothesis: Patients in the music intervention group will have higher number of delirium/coma free days as measured by the Confusion Assessment Method for the ICU (CAM-ICU) at seven days post randomization.

Secondary Specific Aim 1: Test the efficacy of music intervention in *improving delirium severity, pain and anxiety* among mechanically ventilated patients as compared to attention control. Hypotheses: Patients in the music intervention group will have lower delirium severity, pain and anxiety scores as measured by the CAM- ICU-7, Critical Care Pain Observation Tool (CPOT) and Visual Analogue Scale-Anxiety (VAS-A) respectively at seven days post-randomization.

Secondary Specific Aim 2: Test the efficacy of music intervention in *improving the long-term neuro-psychological outcomes* as compared to attention control. Hypotheses: Patients in the music intervention group will have higher cognitive scores as assessed by the Indiana University Telephone Based Assessment of Neuropsychological Status (IU-TBANS), and lower depression and anxiety scores on the Patient Health Questionnaire (PHQ-9) and Generalized Anxiety Disorder (GAD-7) scales at 3 months post hospital discharge.

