- **Delirium/Coma Free Days:** Delirium/coma free days will be the primary outcome for the trial. Delirium/coma free days are the number of days after randomization patients are alive free of delirium and not in coma during the seven-day study intervention phase. This outcome describes the duration of normal cognitive status where the patient is not comatose and does not have delirium and has been utilized in high impact studies. 14-17 We will utilize the Confusion Assessment Method for the ICU (CAM-ICU)75 and the Richmond Agitation Sedation Scale (RASS)⁷⁶ for assessment of delirium and coma respectively. RASS score ranges from -5 to +4 with a score of -4 or -5 (lack of response to verbal or physical stimuli) characterized as comatose and ineligible for CAM-ICU assessments. RASS scores of -3 and -2 depict moderate and light sedation, -1 drowsiness, 0 alert and calm, and +1 to +4 various degrees of agitation. Patients with a RASS score of -3 to +4 will be considered eligible for CAM-ICU assessments. The CAM-ICU score will be determined by examining the patient for (a) acute or fluctuating changes in mental status, (b) inattention, (c) altered level of consciousness and (d) disorganized thinking. Patients will be considered delirious if they display (a), (b), plus (c) and/or (d). Trained research assistants will be performing CAM-ICU twice daily after the assigned intervention. Sedation status through RASS will be collected before and after the intervention delivery. After the 7-day study intervention phase, study staff will continue to assess RASS and CAM-ICU twice daily throughout the subject's hospital stay (up till day 28).
- **2. Delirium Severity**: Delirium severity will be assessed twice daily by trained research assistants using the CAM-ICU-7 developed by [name]. CAM-ICU-7 is a seven-point scale (0-7), derived from the RASS and the CAM-ICU. The CAM-ICU-7 score ranges from 0-7; categorized as 0-2: no delirium, 3-5: mild to moderate delirium, and 6-7: severe delirium. Trained research assistants will be performing CAM-ICU-7 twice daily after the assigned intervention. After the 7-day study intervention phase, study staff will continue to assess CAM-ICU-7 twice daily throughout the subject's hospital stay (up till day 28).

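### Secondary Aim 1 hypothesises lower scores at day 7, but the only term the plan interprets and powers is the group-by-time interaction, so an early, steady benefit could be reported as null

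*Combined protocol and SAP*

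**What the plan says.** The hypothesis, in the Rationale and Specific Aims section, concerns a level at a fixed time: "Patients in the music intervention group will have lower delirium severity, pain and anxiety scores", with the time given as "respectively at seven days post-randomization".

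The analysis, in Statistical Considerations under Secondary Specific Aim 1, is a mixed model of scores taken twice daily from randomization to day 7, death or discharge. On its terms the plan says "Group, time, group and time interactions will be included as independent variables while adjusting for potential baseline covariates". The one sentence that interprets a term is "Significant group and time interactions will indicate differences in changes of these outcomes between the two groups".

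Two further analyses are named: "Post-hoc analyses will be conducted to determine the earliest times when significant differences between these outcomes can be detected" and "We will also examine potential non-linear trajectories of change in these outcomes by including quadratic time in the models and by fitting spline models". Neither is designated as the test of the hypothesis. No day-7 contrast or average group difference is named.

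Under Sample Size and Power, the figures for the three outcomes (VAS-A 83.5%, CPOT 80.6%, CAM-ICU-7 80.6%) are all for the interaction.

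On timing, Study Procedures says of delirium severity: "Trained research assistants will be performing CAM-ICU-7 twice daily after the assigned intervention". CPOT and VAS-A are collected four times daily, before and after sessions.

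**The concern.** A difference in level and a difference in slope are separate quantities. If music lowers scores from the first session and holds them there, the hypothesis is true at day 7 but the interaction is zero. CAM-ICU-7 is most exposed: its first modelled score already follows a session, and the enrollment column of the data-collection schedule is empty for it.

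The trial could then report no effect on delirium severity while scores were lower throughout. With no decision term named, the choice among the group term, the interaction and the post-hoc time points would also be made after the data are seen.

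**Working it through.** **1. The plan's own figures.** The sample size reproduces: 64 per arm gives 80.1% power at 0.5 SD, and 128/(1 - 0.20) = 160. The VAS-A interaction power does not. With 14 half-day scores and AR(1) correlation 0.4 per day, the standard error (SE) of the slope difference is 0.0358 SD per day. Then 0.03/0.0358 = 0.84, or about 13% power. Across seven measurement and test variants, two-sided with 128 patients and 0.03 SD read as a daily change, power is 6-21%, not 83.5%. For CPOT, 0.2 SD per day gives 96-100% with 7, 8 or 14 measures against the stated 80.6%, although its correlation is not stated separately. This is a separate matter; the point below does not depend on it.

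**2. What each test addresses.** Write the mean score as b0 + b1·G + b2·t + b3·G·t. The between-group difference at time t is d(t) = b1 + b3·t. The hypothesis concerns d(7); the interaction tests b3 = 0. Under a constant benefit D, d(t) = -D at every t, so b1 = -D and b3 = 0. Interaction power then equals alpha, 5%, for any D. The same holds with categorical time, because all the interaction terms are zero.

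**3. Set-up for size.** From the documents: 64 per arm (128 in total), twice-daily scores, AR(1) 0.4 per day, alpha 0.05 (two-sided assumed). Assumed here: a 0.4 SD benefit, complete data, and a share s of variance lying between patients. The correlation is s + (1 - s)·0.4^|ti - tj|; the covariance of the two differences (intercept and slope) is (2/64)(X'R⁻¹X)⁻¹; power is approximately Φ(difference/SE - 1.96).

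| s | SE slope | SE day 7, straight line* | SE average |
|---|---|---|---|
| 0 | 0.036 | 0.147-0.161 | 0.089 |
| 0.3 | 0.030 | 0.156-0.166 | 0.122 |
| 0.5 | 0.025 | 0.162-0.169 | 0.140 |

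*Lower value: last score at day 7. Upper value: last score at day 6.5, extrapolated to day 7.

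**4. Constant 0.4 SD benefit.**
- Interaction: 5%.
- Day 7, straight line: 0.4/0.147 = 2.72 gives 78%; 0.4/0.169 = 2.37 gives 66%.
- Average: 0.4/0.089 = 4.49 gives 99%; 0.4/0.140 = 2.86 gives 82%.
- Day 7, fully categorical time: SE = √(2/64) = 0.177, and 0.4/0.177 = 2.26 gives 62%.

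An independent check at 0.5 SD with 7 daily scores and 10,000 simulated trials gave 5.3% for the interaction, 80.0% for observed day-7 scores and 90.4% for the straight-line day-7 contrast.

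**5. Benefit reached by day 1, then flat at 0.4 SD.** A straight-line fit estimates 0.44-0.50 SD at day 7, depending on time coding, against a true 0.40. Its apparent power there is inflated by misfit and is not used as evidence.

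**6. Linear build-up to 0.4 SD at day 7.** The slope is 0.4/7 = 0.057 SD per day.
- s = 0: 0.057/0.0358 = 1.60, 36% for the interaction against 70-78% at day 7.
- s = 0.5: 0.057/0.0253 = 2.26, 62% against 66-69%.
- s = 0.7 (SE slope 0.0196): 0.057/0.0196 = 2.9, 83% against 64-66%.

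The ordering reverses somewhere above a 50% share.

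**7. CPOT and VAS-A.** If the first pre-session score enters as an outcome, a step benefit does create an interaction. At 0.5 SD and correlation 0.4, power is 26-35% with linear time and 50-82% with categorical time. At correlation 0.7 it is 42-46% and 78-99.8%. Whether that score enters is open, since the analysis models two scores a day and four are collected.

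**The case against.** A reader might infer that efficacy will be judged on the interaction alone, so that a real benefit on all three outcomes would be missed. The documents do not support that. The plan says the models compare the scores, the group term is present, and time-point comparisons are planned. The interaction sentence says what an interaction means; it does not make it the sole criterion. A constant difference would be visible in the output. What stands is that none of these routes is designated as the test, and that with an interaction in the model the group coefficient is the difference at time zero, not at day 7.

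A reader might also infer that a day-7 contrast always has at least the interaction's power. Step 6 shows otherwise, and the documents give no between-patient share to settle it. The plan cites an earlier trial in which VAS-A change appeared linear, the pattern that suits the interaction best.

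Pre-session CAM-ICU-7 values may exist, because eligible patients are screened with it before being approached. But the model runs from randomization, and the plan does not say those values enter it.

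Finally, the calculation assumes complete data, whereas each series ends at death or discharge. Suppose, for illustration, that of 64 per arm 20% leave after day 2 and another 20% after day 4. Day-7 power for a constant 0.4 SD then falls to about 56-59% with a straight line, and 42-47% with categorical time (SE 0.211-0.228). That is a real cost, though the interaction stays at 5% for the same benefit.

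**Conclusion.** The mismatch holds. The hypothesis is a day-7 level; the only interpreted and powered term is a difference in change. For a series with no pre-session score, as CAM-ICU-7 is described, the 5% result for a constant benefit is algebra and needs no assumption about effect size. The 66-78% and 82-99% comparators rest on an illustrative 0.4 SD, 64 per arm, complete data, AR(1) 0.4 per day and a between-patient share of 0-50%. For CPOT and VAS-A the loss is partial and turns on modelling choices the plan leaves open.

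The case for change is that the test should match the stated hypothesis, not that it is uniformly more powerful. These are secondary outcomes, so the primary conclusion is unaffected, but the plan should be corrected before analysis.

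**What to change.** Keep the mixed model and the data. For CAM-ICU-7, CPOT and VAS-A, prespecify the model-estimated between-group difference at day 7 as the test of the hypothesis. Take it from a model with categorical or spline time. Do not use the group coefficient plus seven times the interaction from a straight line, which overshoots when benefit plateaus early.

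Report the average difference over days 1-7 as supportive and the interaction as a description of the time pattern. State which of the four daily CPOT and VAS-A scores enter the model, and whether a pre-session score is an outcome or a covariate.

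The cost is plan wording and one contrast per model, with no new data. The downside is lower precision at day 7, from flexible time (62% against 66-78% in the example) and from patients leaving by death or discharge.
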